3.3 Evaluation Criteria/Effectiveness

The CHANGE IN PRACTICE therapy regimen (which includes therapy with The MetaNeb® System) will be evaluated to determine if there is a decrease in the number of patients who experience Significant Postoperative Pulmonary Complications among the group of patients treated with The MetaNeb® System. Endpoints are described below:

Primary Endpoint:

Significant Postoperative Pulmonary Complication (PPC):

One or more of the following that occurs within seven (7) days of the post-surgical admission will be considered a Significant Postoperative Pulmonary Complication (PPC)

- **Patient Requires Prolonged Mechanical Ventilation:**

Defined as patient requirement for invasive mechanical ventilation (MV) for > 24 hours (after hour 24) post-operatively. This includes patients that require re-intubation and MV after hour 24, regardless of length of time on MV in the first 24 hours postoperatively.

Hill-Rom®	Evaluation of a practice change to include The MetaNeb® System to reduce postoperative pulmonary complications	Page 17 of 31
CBI	8 September 2016	Rev C Protocol #: CR-RR2015-001

- **Patient requires prolonged respiratory support for > 24 hours from post-surgical admission**
 - Requirement for non-invasive ventilation (NIV) above patient's baseline requirement after hour 24, or continuous positive airway pressure (CPAP) above patient's baseline requirement after hour 24.
 - Requirement for O₂ therapy > 40 % FiO₂ or > 5 LPM via NC (and above patient's baseline) after hour 24 postoperatively.
- **Diagnosis of Pneumonia Within Seven (7) Days**
 - Physician documented pneumonia AND
 - Radiologists report indicating pneumonia / new or expanded infiltrate AND
 - Elevated or low Temperature (> 38° C or < 36° C, or as defined by the site) and/or elevated white count above the upper level of normal as defined by the site
- **Readmission to ICU (or transfer to an elevated level of care) for pulmonary complications within seven (7) days of the post-surgical hospital admission**

Defined as readmission to the ICU within seven days of post-surgical hospital admission or readmission to an elevated care unit such as special care or ICU step-down unit after being moved to a lower (e.g. general care) floor (e.g. patient discharged from ICU on day 4 at 0800 is readmitted to the ICU before day 8 at 0800).

Secondary Endpoints:

- **Requirement for invasive mechanical ventilation for > 48 hours within seven (7) days of the post-surgical hospital admission**

Defined as patient requirement for invasive mechanical ventilation (MV) for > 48 hours (after hour 48) post-operatively. This includes patients that require re-intubation after hour 48, regardless of length of time on MV in the first 48 hours postoperatively.
- **Requirement for respiratory support for > 48 hours within seven (7) days of the post-surgical hospital admission**

Respiratory support greater than the patient's baseline level for a period longer than 48 hours

 - Requirement for non-invasive ventilation (NIV) above patient's baseline requirement after hour 48 from post-surgical admission or continuous positive airway pressure (CPAP) above patient's baseline requirement after hour 48.
 - Requirement for O₂ therapy > 40 % FiO₂ or > 5 LPM pm via Nasal Cannula (and above patient's baseline) after hour 48 postoperatively.

Hill-Rom®	Evaluation of a practice change to include The MetaNeb® System to reduce postoperative pulmonary complications	Page 18 of 31
CBI	8 September 2016	Rev C

- **ICU Length of Stay (LOS)**

ICU length of stay, during initial hospital stay, will be determined by calculating the number of days/hours spent in ICU. The following will be documented:

- Time of admission to the ICU to actual time of initial discharge from the ICU during initial hospital stay
- Total ICU days/hours (includes readmissions) during initial hospital stay

- **Hospital Length of Stay (LOS)**

Hospital length of stay will be determined by calculating the number of days/hours spent in hospital. The following will be documented:

- Time of admission to time of discharge from the hospital (total days/hours)

- **Time on Mechanical Ventilation**

Time on mechanical ventilation, during the initial hospital stay, will be documented as follows:

- Time to initial extubation from time of initial intubation, if initial intubation was placed after surgery; or from time of post-surgical admission, if intubation was in place prior to start of surgery
- Total time on invasive mechanical ventilation - will be determined for each patient by calculating the total number of days/hours intubated and mechanically ventilated from the time of post-surgical admission until the time of initial hospital discharge.
- Total time on non-invasive ventilation - will be determined for each patient by calculating the total number of days/hours ordered for non-invasive ventilation from the time of post-surgical admission to the hospital unit until the time of initial hospital discharge.

- **Readmission to ICU and transfers to elevated level of care for pulmonary complications**

Readmissions to ICU and transfers to an elevated level of care, during the initial hospital stay, will be documented for each event. The following will be documented:

- Number of readmission to ICU or elevated level of care events

Hill-Rom®	Evaluation of a practice change to include The MetaNeb® System to reduce postoperative pulmonary complications	Page 19 of 31
CBI	8 September 2016	Rev C

- Number of patients requiring readmission to the ICU or to an elevated level of care
- **Readmission to Hospital**
Hospital records will be reviewed at each site, 30 days after the last patient has been discharged from the hospital. Readmissions, for any cause, within 30 day of discharge for any study patient will be documented.

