3.2 Study Population

The study population consists of adult post-surgical patients who have undergone thoracic, aortic or upper abdominal surgery who are at high risk for PPCs.

3.2.1 Inclusion Criteria:

Patients who meet all of the following criteria will be included in the study:

- Age \geq 18 years
- Post-thoracic, -upper abdominal or -aortic surgery
- Open surgical procedure
- Incision at or above the umbilicus
- High risk defined by:
 - Documented ASA class \geq 3

Hill-Rom®	Evaluation of a practice change to include The MetaNeb® System to reduce postoperative pulmonary complications			Page 16 of 31
	CBI	8 September 2016	Rev C	Protocol #: CR-RR2015- 001

OR

- Documented ASA class 2 **AND** One or more of the following:
 - Current Smoker or Smoking history within past 6 months
 - History of COPD
 - Documented Obesity and/or BMI $\geq 30 \text{ kg/m}^2$
 - Age ≥ 75

3.2.2 Exclusion Criteria:

Patients who meet any of the following criteria will be excluded (or will be exited) from the study:

- Contraindication to Continuous High Frequency Oscillation (CHFO) therapy (e.g. untreated tension pneumothorax)
- Minimally invasive or “...scopic” surgical procedure
- Spinal surgery involving a posterior approach
- Surgery for organ transplant
- Chronic invasive Positive Pressure Ventilation (PPV) therapy

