3.4.1 Study Observations Table Detailed Description

Hill-Rom®	Evaluation of a practice change to include The MetaNeb® System to reduce postoperative pulmonary complications			Page 20 of 31
	CBI	8 September 2016	Rev C	Protocol #: CR-RR2015- 001

Documentation of observations will be completed by study staff based on review of the patient's medical records. A detailed description of documentation requirements for each parameter is below.

Demographic Data: The following data will be recorded from the patient medical record: Age, Height, Weight, Race, Gender, ASA score, Documented obesity and/or $BMI \geq 30 \text{ kg m}^2$.

Medical History: Pulmonary history will be recorded from the patient medical record including: Asthma, Cystic Fibrosis, Bronchiectasis, COPD, Neuromuscular Disease, Other Pulmonary Condition(s), Obstructive Sleep Apnea

Pre-surgery Respiratory Status: Pre-surgery respiratory status such as Invasive Mechanical Ventilation, Non-invasive Mechanical Ventilation, CPAP, Supplemental oxygen will be recorded.

Post-Surgery Data (day 0): Following surgery, the albumin level (if available in the medical record) and surgery type will be recorded.

Location: The post-surgery location of each patient upon return to the hospital unit or floor (ICU, General Care, etc.) will be recorded. The patient's location during the first seven days, or until the time of discharge from the hospital, whichever occurs first, will also be recorded at regular intervals based on entries in the medical record.

Respiratory Status: The respiratory status of each patient, following surgery will be recorded. Respiratory status during the first seven days, or until the time of discharge from the hospital, whichever occurs first, will also be recorded at regular intervals based on entries in the medical record. Respiratory status will include documentation of the mode of support, the device in use and the settings.

Respiratory Milestones: Key respiratory milestones that occur each day will be recorded based on entries in the medical record. These include 1) extubation, 2) re-intubation, 3) return to baseline respiratory support, 4) Diagnosis of Pneumonia and 5) Readmission to the ICU or an elevated level of care. These milestones will be recorded for each day until discharge from the hospital, or through day seven (7) following the day of surgery, whichever occurs first.

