## 2 STUDY OBJECTIVES AND ENDPOINTS

### 2.1 Primary Objective and Endpoint

The primary objective of Stage I of this study is to estimate the incidence of postoperative pulmonary complications (PPC) in post-surgical patients receiving standard of care per hospital and respiratory care department procedures and policies.

The primary objective of Stage II of this study is to estimate the incidence of PPC in post-surgical patients receiving change in practice therapy regimen, which includes the addition of the MetaNeb® System to the standard of care per hospital and respiratory care department procedures and policies.

The primary endpoint at each stage is to evaluate the proportion of subjects who experience a significant PPC within seven (7) days of: post-surgical hospital admission (Stage I) or post-surgical hospital admission and MetaNeb® System administration (Stage II). A PPC is defined as having one or more of the following:

- 1. Patient requires prolonged mechanical ventilation for > 24 hours**  
Invasive mechanical ventilation (MV) for > 24 hours from post-surgical hospital admission (PSHA)
- 2. Patient requires prolonged respiratory support for > 24 hours from PSHA**

- Requirement for non-invasive ventilation (NI V) or continuous positive airway pressure (CPAP) above patient's baseline requirement, not related to obstructive sleep apnea (OSA), for > 24 hours from PSHA
- Requirement for O2 therapy > 40 % FiO2 or > 5 LPM via NC (and above patient's baseline), for > 24 hours from PSHA

3. **Diagnosis of Pneumonia within 7 days from PSHA**
  - Physician documented pneumonia, and
  - Radiologists report indicating pneumonia / new or expanded infiltrate, and
  - Elevated or low Temperature (> 38° C or < 36° C, or as defined by the site) and/or elevated white count above the upper level of normal as defined by the site
4. **Readmission to ICU (or transfer to an elevated level of care) for pulmonary complications**  
Defined as readmission to the ICU or readmission to an elevated care unit within 7 days from PSHA

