#### **5. Time on Mechanical Ventilation**

Time on mechanical ventilation, during the initial hospital stay, will be documented as follows:

- Time to initial extubation
- Total time on invasive mechanical ventilation - will be determined for each patient by calculating the total number of days/hours intubated and mechanically ventilated from the time of PSHA until the time of initial hospital discharge.
- Total time on non-invasive ventilation - will be determined for each patient by calculating the total number of days/hours ordered for non-invasive ventilation from the time of PSHA until the time of initial hospital discharge.

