### 6.1 Description of Analytical Methods

#### 6.1.1 Derived Variables

**Primary Endpoint:** occurrence of a postoperative pulmonary complication (PPC).

Stage I: during the 7 days post-surgery hospital admission (PSHA)

Stage II: during the 7 days PSHA. Event must occur after MetaNeb® administration.

For each subject, occurrence of a PPC will be set to yes if one or more of the four conditions below occur.

- i. **PPCflg1:** Patient Requires Prolonged Mechanical Ventilation beyond Hour 24 from PSHA.

Duration of invasive mechanical ventilation (IMV) is defined as IMV stop time minus IMV start time where:

IMV Start Time=date & time of the later of start of IMV or PSHA

IMV Stop Time=date & time of the earlier of stop of IMV or PSHA+7

If IMV is required on more than one occasion during the 7 days following PSHA, then the cumulative sum will be calculated.

$$\text{PPCflg1} = \begin{cases} 1 & \text{if the latest IMV stop time is more than 24 hours after PSHA} \\ 0 & \text{otherwise} \end{cases}$$

If IMV start date is available, but the start time is missing, then a clock time consistent with the earliest possible time of the day will be imputed, ex. Hour 00.00 or PSHA clock time.

If the IMV stop date is available, but the stop time is missing, then the IMV stop time will be taken as the assessment time.

- ii. **PPCflg2:** Patient Requires Prolonged Respiratory Support beyond Hour 24 from PSHA

- a) Duration of non-invasive MV (NIMV) is defined as NIMV Stop time minus NIMV start time. NIMV start and stop times are defined similarly to those of IMV.

Imputations for missing NIMV start or stop times will be used similarly to those of IMV.

- b) Duration of CPAP is defined as CPAP Stop time minus CPAP Start time.

- c) Duration of O2 therapy [if >40% FiO2 or >5 LPM via Nasal Cannula] will be calculated similarly.

Duration of respiratory support is defined as the sum of durations of NIMV, CPAP, and O2 therapy during the 7 days following hospital admission.

$$\text{PPCflg2} = \begin{cases} 1 & \text{if the latest NIMV, CPAP, or O2 therapy stop time} \\ & \text{is more than 24 hours after PSHA} \\ 0 & \text{otherwise} \end{cases}$$

- iii. **PPCflg3:** Diagnosis of pneumonia

- iv. **PPCflg4:** Readmission to ICU (or transfer to an elevated care) for PPC with 7 days of PSHA

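### Total time on NIV is not limited to NIV above baseline, so a small stage imbalance in pre-surgery NIV users can mask or mimic a modest change in its mean

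*Protocol*

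**What the plan says.** **The endpoint.** Under the secondary endpoint on time on mechanical ventilation, Protocol 3.3 obtains total NIV time by "calculating the total number of days/hours ordered for non-invasive ventilation from the time of post-surgical admission to the hospital unit", ending at initial discharge. SAP 2.2 item 5 matches it: "calculating the total number of days/hours ordered for non-invasive ventilation from the time of PSHA until the time of initial hospital discharge". Neither text mentions the patient's baseline.

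**The neighbouring endpoints.** For the primary endpoint, Protocol 3.3 asks for "Requirement for non-invasive ventilation (NIV) above patient's baseline requirement after hour 24". SAP 2.1 counts NIV or CPAP only when it is "above patient's baseline requirement, not related to obstructive sleep apnea (OSA), for > 24 hours from PSHA". The 48-hour respiratory-support endpoint also carries a baseline condition in both documents.

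**Eligibility.** The only exclusion for long-term ventilation (Protocol 3.2.2) is "Chronic invasive Positive Pressure Ventilation (PPV) therapy". COPD and obesity are among the routes into the study for ASA class 2 patients.

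**Data and analysis.** Protocol 3.4.1 states: "Pre-surgery respiratory status such as Invasive Mechanical Ventilation, Non-invasive Mechanical Ventilation, CPAP, Supplemental oxygen will be recorded". SAP 6.1.6 tabulates that status. SAP 6.1.1 says: "Duration of non-invasive MV (NIMV) is defined as NIMV Stop time minus NIMV start time". SAP 6.3 reports mean, median and SD for time on mechanical ventilation, without adjustment. Protocol 3.5.2 plans to compare the stages in order to find associations attributable to the device.

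**The concern.** Elsewhere the definitions treat a patient's usual respiratory support as something other than an outcome. The invasive-ventilation total is protected in the same way, because chronic invasive ventilation is excluded. The NIV total has neither protection. A patient who uses NIV every night at home, and has it ordered in hospital, adds hours on every night of the stay that have nothing to do with the device.

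A few such patients carry much of the mean and SD of a variable that is zero for most patients. Nothing in a non-randomised before-and-after design balances their number between stages. The difference in mean NIV time, which the protocol intends to read as a possible device effect, would then partly reflect who was enrolled.

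**Working it through.** **Is the gap closed elsewhere in the SAP?**
- SAP 6.1.1 computes NIV duration as stop minus start and subtracts nothing for baseline use.
- The paragraph on secondary derivations at the end of SAP 6.1.1 carries the primary-endpoint logic over only to incidence beyond 48 hours. It adds a rule for time to extubation but none for NIV time.
- SAP 6.1.6 tabulates pre-surgery NIV but does not use it to subtract, stratify or adjust.

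The gap is therefore not closed.

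**Inputs.** About 200 patients per stage comes from the Protocol synopsis. The documents give no expected NIV time, no prevalence of pre-surgery NIV and no effect on NIV time, so there is no stated figure to reproduce. All other inputs are assumptions:
- H, hours of usual NIV ordered per user during the stay: 8 h x 7 nights = 56 h (range 24 to 80 h)
- q, share of patients with new postoperative NIV: 8% to 10%
- D, hours of new NIV per such patient: 24 h
- p, share of patients on NIV before surgery
- r, relative reduction in new NIV

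**Formulas.** Mean NIV hours per patient = p x H + q x D. Shift from imbalance = (p2 - p1) x H. True effect = r x q x D. Break-even imbalance = r x q x D / H.

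**Shift from imbalance at H = 56 h.** 1, 2 or 3 points (2, 4 or 6 of 200 patients) shift the mean by 0.56, 1.12 or 1.68 h. For 2 points, the range over H = 24 to 80 h is 0.48 to 1.60 h.

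**True effect and break-even at H = 56 h:**

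| Reduction in new NIV | q = 8% (mean 0.08 x 24 = 1.92 h) | q = 10% (mean 0.10 x 24 = 2.40 h) |
|---|---|---|
| 25% | 0.48 h; 0.9 points | 0.60 h; 1.1 points |
| 50% | 0.96 h; 1.7 points (3.4 patients) | 1.20 h; 2.1 points (4.3 patients) |
| 100% | 1.92 h; 3.4 points | 2.40 h; 4.3 points |

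For a halving, break-even depends on H. At 24 h it is 0.96/24 = 4.0 to 1.20/24 = 5.0 points; at 80 h it is 1.2 to 1.5 points.

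**Masking.** Let pre-surgery users go from 3% to 5% while new NIV is halved.
- q from 10% to 5%: Stage I is 1.68 + 2.40 = 4.08 h and Stage II is 2.80 + 1.20 = 4.00 h. A true fall of 1.20 h appears as 0.08 h.
- q from 8% to 4%: 1.68 + 1.92 = 3.60 h becomes 2.80 + 0.96 = 3.76 h, a small rise.

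**Mimicking.** Let users go from 5% to 3% with q fixed at 10%. Then 5.20 h becomes 4.08 h, a fall of 1.12 h with no effect at all.

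**SD.** Take fixed hours and independence, with p = 3% and q = 10%. The variance is 0.03 x 0.97 x 56² + 0.10 x 0.90 x 24² = 91.3 + 51.8 = 143.1, so the SD is 12.0 h. Without usual NIV it is 7.2 h.

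**How often would 2 points occur by chance?** The SD of the stage difference is sqrt(2p(1-p)/200), or 1.0, 1.7 and 2.2 points at p = 1%, 3% and 5%. A difference of at least 2 points in either direction has probability of about 4%, 24% and 36% (normal approximation).

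**Sensitivity.** The grid used imbalance of 1-3 points, H of 24/56/80 h, q of 5/10/15% and D of 12/24/48 h. The imbalance exceeds a 25% reduction in 53 of 81 settings, a 50% reduction in 31 and complete removal in 13.

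**The case against.** A reader might infer that a small difference in home-NIV users can outweigh any change in postoperative NIV, or that the endpoint mainly measures case mix. The documents supply no figures for this, and the arithmetic does not bear it out. At 2 points the shift of 1.12 h is below the 1.92 to 2.40 h of complete removal, and most grid settings do not overturn a halving. A sign reversal that needs users to double from 5% to 10% does not rest on a small difference.

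Other objections have force:
- SAP 6.3 also gives the median. If fewer than half of patients have NIV ordered, it is 0 in both stages, so only the mean and SD are affected.
- The endpoint counts ordered time. The documents do not say whether a patient's own NIV is ordered in hospital; if it is not, little is added.
- Sleep apnoea is a weak basis for the point. CPAP is listed separately from NIV, so it is unclear whether home CPAP enters the total. In SAP 2.2 item 2 the sleep-apnoea clause attaches to CPAP only.
- The contrast is with the endpoint definitions. The programmed 24-hour flag in SAP 6.1.1 does not state the baseline condition either.
- SAP 6.1.6 would let a reader see an imbalance, though not remove it from the mean.
- Total use could be a deliberate resource measure, like length of stay. Neither document says so, and the stated objective is pulmonary complications.

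These narrow the point but leave the missing baseline condition in place.

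**Conclusion.** The point holds as a minor one about a secondary, descriptive endpoint. Total NIV time counts usual NIV wherever it is ordered in hospital, long-term NIV users are eligible, and no planned analysis separates them. Under the assumed values, about 2 points of imbalance (about 4 of 200 patients) cancels a halving of new NIV in the mean, or produces a difference of that order where there is none. It does not cancel complete removal.

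The size rests on assumed hours, prevalence and new-NIV rates, and it roughly halves or grows by 40% across H = 24 to 80 h. The definition of the primary endpoint has the baseline restriction and is not affected by this gap.

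**What to change.** In SAP 6.3, present total NIV time by stage separately for patients with and without NIV before surgery, and base the Stage I versus Stage II comparison on those without. This removes the (p2 - p1) x H term. In Protocol 3.3 and SAP 2.2 item 5, state whether CPAP is part of the total.

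Simply redefining the total as NIV above baseline would not work to discharge. Settings and the return-to-baseline milestone are specified only through day 7 (Protocol 3.4.1). After that, only start and stop times of mechanical ventilation are specified, and sleep apnoea is recorded as history, not as the reason for an episode. An above-baseline total may be added for days 0-7.

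Cost: a few sentences and one table split, with no new data, because pre-surgery status is collected in both stages. The main comparison leaves out the few baseline NIV users, so it says nothing about change in their NIV time.

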3.4 Study Observations Table

The study observations and documentation timeline is outlined in Table 1.

Table 1. Study Observations Table

Day	Pre-Surgery	Day of Surgery	Post Surgery Day 1 - Day 7	Hospital Discharge	Early Term	Day 30 Post Discharge
Selection Criteria / Enrollment	X					
Informed Consent *	X					
Demographic Data	X					
Medical History	X					
Pre-Surgery Respiratory Status (Patient's Baseline)	X					
Post-Surgical Data (day 0) at day of surgery.		X				
Location (7A & 7P)		X	X			
Respiratory Status (Each Shift)		X	X			
Respiratory Milestones		X	X			
Respiratory Treatments		X	X			
Hospital Discharge Summary				X		
ICU Admission/Discharge Summary (Day 8 - Discharge)				X		
Discharge Respiratory Summary (Day 8 - Discharge)				X		
30-day Readmission					X	
Study Exit Form				X	X	

* Informed consent will be obtained only for subjects in Stage II.

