3.0 Study Design

3.1 Overview of Study Design

3.1.1 Design:

This is a non-randomized facility level pre-post intervention study conducted in two stages for the primary purpose of evaluating the effect of The MetaNeb® System on postoperative pulmonary complications in high risk patients undergoing thoracic and

Hill-Rom®	Evaluation of a practice change to include The MetaNeb® System to reduce postoperative pulmonary complications	Page 13 of 31
CBI	8 September 2016	Rev C Protocol #: CR-RR2015-001

abdominal surgeries. The study will be conducted in two to four (2-4) tertiary academic medical facilities in the US that have not previously used The MetaNeb® System in post-thoracic, post-aortic, or post-upper abdominal surgery patients. After assessing outcomes during a baseline period, therapy with The MetaNeb® System will be introduced and incorporated into the respiratory care treatment regimens and outcomes will be assessed after the change in practice.

3.1.2 Procedure:

In Stage I of the study, a retrospective review of medical records for post-surgical patients, who received STANDARD THERAPY as defined by current hospital and Respiratory Care department policies and procedures. This will be a retrospective data collection only.

The purpose of study Stage I is to estimate the incidence of postoperative pulmonary complications in post-surgical patients receiving standard of care per hospital and Respiratory Care department procedures and policies. Data collected in Stage I will include data from the medical records of 200 randomly selected, eligible patients treated during the year prior to the CHANGE IN PRACTICE. This allows for inclusion of patients from the seasonally consistent time period as well as those from most recent time period, during which care practices are most similar.

In Stage II, a CHANGE IN PRACTICE will be made and patients will receive standard care with the addition of therapy with The MetaNeb® System. Other standard airway clearance and lung expansion therapies typically delivered by Respiratory Therapy will not be delivered during Stage II. During Stage II, data from approximately 200 patients will be collected from the medical records across the 3 sites.

Demographic, clinical & outcome data will be collected for eligible patients during the two stages of the study. Study staff will collect data from the medical records, following a protocol determined schedule.

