5.0 Study Procedures

5.1 Informed Consent:

A waiver of informed consent will be requested for patients enrolled in the study in Stage I (retrospective review of data). Informed consent must be obtained from all subjects in Stage II prior to participation as per Federal Regulations and/or the qualifying Institutional Review Board (IRB). A blank copy of the IRB-approved form must be kept on-site and by the sponsor. The signed original for each subject must be kept in the study files.

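### Stage II takes only consenting patients while Stage I is a chart sample under a requested waiver; case mix may differ between stages, and the SAP plans only crude proportions

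*Protocol*

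**What the plan says.** **Entry.** Stage I draws on the "medical records of 200 randomly selected, eligible patients treated during the year prior to the CHANGE IN PRACTICE" (Protocol 3.1.2), and Protocol 5.1 says a consent waiver will be requested for it. For Stage II, Protocol 5.1 states: "Informed consent must be obtained from all subjects in Stage II prior to participation", subject to federal regulations and/or the IRB. The footnote to Table 1 (Protocol 3.4) says: "Informed consent will be obtained only for subjects in Stage II". The consent mark sits in the pre-surgery column of both the protocol and SAP tables.

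**Eligibility.** One list serves both stages (Protocol 3.2). Its only exclusion for ventilation is "Chronic invasive Positive Pressure Ventilation (PPV) therapy". Other patients ventilated before surgery are foreseen. Protocol 3.4.1 says "Pre-surgery respiratory status such as Invasive Mechanical Ventilation, Non-invasive Mechanical Ventilation, CPAP, Supplemental oxygen will be recorded", SAP 6.1.6 tabulates that status, and the ventilation-time endpoint in Protocol 3.3 provides for a tube already in place before the operation.

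**Endpoint.** The invasive ventilation component is "Defined as patient requirement for invasive mechanical ventilation (MV) for > 24 hours (after hour 24) post-operatively". In Protocol 3.3 and SAP 2.1, non-invasive ventilation, CPAP and oxygen count only when above the patient's own baseline; invasive ventilation carries no such condition. The derivation in SAP 6.1.1 applies a baseline condition to no modality at all.

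**Analysis.** Protocol 3.5.2 plans a stage comparison to find associations attributable to the device and leaves the choice of subsets to the SAP. SAP 6.3 names no subset, restriction or model for the endpoint, only proportions with 95% intervals. SAP 6.1.2 counts enrolled subjects only. SAP 1 says Stage II follows the analysis of Stage I data.

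**The concern.** A patient who would refuse, or could not give, consent can be in the Stage I sample and absent from Stage II. The stages could then differ in who was studied as well as in how they were treated, and a crude comparison cannot separate the two.

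Patients invasively ventilated before surgery matter most because the direction can be argued from the plan's own definitions. They may be harder to consent in person, and they can meet the primary endpoint through ventilation that began before either regimen was given. If they are scarcer in Stage II, the Stage II rate falls without any device effect. For refusers and other non-consenting patients the documents give no basis for a direction.

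**Working it through.** The plan has no figure on this point to reproduce: SAP 5 says the sample size was not formally derived, and no count, event risk or consent rate is given for this group.

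**Inputs from the documents.** About 200 patients per stage (Protocol synopsis); Stage I rate R between 5% and 15% (Protocol 3.5.1). The 12% used below is an illustrative value inside that range.

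**Assumptions.** m = 2, 4 or 8 patients ventilated before surgery among 200 Stage I charts; their event risk q = 50% or 100%; none of them in Stage II; no device effect.

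**Spurious difference.** Stage I satisfies 200R = mq + (200 − m)p0, where p0 is the risk in all other patients and hence the Stage II rate. So p0 = (200R − mq)/(200 − m), and D = R − p0 = m(q − R)/(200 − m).

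**95% half-width at the scenario's own rates.** H = 1.96 × √[R(1 − R)/200 + p0(1 − p0)/200].

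D, with H in brackets, in percentage points:

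| R | q | m = 2 | m = 4 | m = 8 |
|---|---|---|---|---|
| 5% | 50% | 0.45 (4.18) | 0.92 (4.08) | 1.88 (3.87) |
| 5% | 100% | 0.96 (4.07) | 1.94 (3.85) | **3.96 (3.33)** |
| 10% | 50% | 0.40 (5.83) | 0.82 (5.77) | 1.67 (5.65) |
| 10% | 100% | 0.91 (5.76) | 1.84 (5.63) | 3.75 (5.34) |
| 12% | 50% | 0.38 (6.32) | 0.78 (6.28) | 1.58 (6.18) |
| 12% | 100% | 0.89 (6.27) | 1.80 (6.15) | 3.67 (5.91) |
| 15% | 50% | 0.35 (6.96) | 0.71 (6.93) | 1.46 (6.85) |
| 15% | 100% | 0.86 (6.91) | 1.73 (6.83) | 3.54 (6.63) |

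The range is 0.35 to 3.96 points. D exceeds H only in the bold cell, where p0 = (10 − 8)/192 = 1.04% and 8 of the 10 Stage I events come from this group.

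**Partial entry.** With m/2 such patients in Stage II, its rate is p0 + (m/2)(q − p0)/200, against p0 + m(q − p0)/200 in Stage I. D halves, to 0.18-1.98 points. With equal numbers D = 0.

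**How many would be needed.** At R = 12%, D = H when p0 = 6.37%, where both equal 5.63 points. Then m = 200 × 0.0563/(q − 0.0637): 25.8 at q = 50%, 16.4 at 75% and 12.0 at 100%, or about 12-26 patients in 200.

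**Precision cost of restriction.** Removing 8 Stage I charts at R = 12% moves the half-width from 1.96 × √[0.12 × 0.88 × (1/200 + 1/200)] = 6.37 points to 1.96 × √[0.12 × 0.88 × (1/192 + 1/200)] = 6.44 points.

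**The case against.** The strongest objection is that the consent barrier is inferred. Protocol 5.1 asks for consent before participation, not before surgery, and defers to federal rules and the IRB. The device is used after surgery, so surrogate or later consent is not ruled out, and consent forms were not available for this review. The table column is weak evidence: some marks, such as the one for 30-day readmission, sit in different columns in the two tables. This stands. A reader might infer that ventilated patients cannot enter Stage II; the documents do not say so.

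A second objection is that the size is wholly assumed. This also stands, and it cuts both ways. If 20 of 200 Stage I charts (10%) were such patients with 80-100% risk, against 10% in everyone else and none in Stage II, the difference would be 0.10 × (0.80 − 0.10) = 7.0 to 0.10 × (1.00 − 0.10) = 9.0 points.

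Third, pre-surgery ventilation is recorded and tabulated, so an imbalance could be seen. That is so, but a table reveals an imbalance without correcting the comparison.

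Finally, unequal consent is inherent in an openly retrospective-prospective design, and the lack of any adjusted comparison is a wider SAP gap than consent alone. Both are fair. They are reasons to keep the request small, not to leave the comparison crude.

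**Conclusion.** The point holds as a possible difference in case mix that the analysis plan does not address. The difference in entry, the shared criteria and the crude analysis are documented; under-representation of ventilated patients in Stage II is an inference.

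Under the stated assumptions the bias is modest, 0.35 to 3.96 points in the device's favour. A reader might infer that it could by itself produce a positive result. Within the assumed grid that is supported only in the 5%, 8-patient, all-events corner. The opposite inference, that it never matters, fails as well: at 10% with 8 patients, all events, D is 3.75/5.34 = 70% of the half-width and would add to any chance difference.

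Nor should a reader conclude that every modality except invasive ventilation is protected by a baseline condition. That contrast holds in Protocol 3.3 and SAP 2.1 but not in the SAP 6.1.1 derivation, and the two need reconciling.

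This is worth changing before Stage II, but it does not invalidate the study.

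**What to change.** In the SAP, before Stage II starts:

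1. Add a stage comparison that excludes patients invasively ventilated before surgery from both stages, reported beside the unrestricted comparison. The field is already collected, and SAP 6.1.6 will show the Stage I count in time.
2. Add one supportive adjusted stage comparison using baseline items already collected, for example ASA class (2 levels), surgery type (3 levels) and site. With 2-4 sites this takes 1 + 1 + 2 + (1 to 3) = 5-7 parameters including stage. At 400 × 5% = 20 to 400 × 15% = 60 events, with the same rate in both stages, that is 2.9-12 events per parameter. If events are near 20, drop surgery type (3-5 parameters, 4.0-6.7 events each). State that this model addresses general case mix and not the ventilated group, for which it has no term.
3. In SAP 6.1.2, report Stage II counts of patients eligible, approached, consented and not consented.

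The cost is SAP wording, a small logging task and slightly fewer charts in the restricted analysis (6.37 to 6.44 points in the example above). No new data field is needed. Refusal bias can be described from the log but not removed, and the adjusted result will be weak if events are few.
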